#### 8. Laboratory Procedures and Assessments

#### 8.1. Complete Blood Count (CBC)

The CBC will include the following: hemoglobin, hematocrit, platelet count, RBC, WBC with differential (neutrophils, lymphocytes, monocytes, eosinophils, basophils and other cells).

# 8.2. Coagulation Profile

A coagulation profile will include activated partial thromboplastin time (aPTT), prothrombin time (PT), and an international normalized ratio (INR).

# 8.3. Serum Chemistry

Serum chemistry will include electrolytes (sodium, potassium, chloride and bicarbonate), BUN, serum creatinine, glucose, bilirubin, AST, ALT, alkaline phosphatase, LDH, uric acid, total protein, albumin, calcium, magnesium and phosphate.

## 8.4. Urine or Serum Pregnancy Test

A urine or serum pregnancy test will be obtained for all females of childbearing potential. Exempt female patients will include those who have undergone a bilateral oophorectomy or hysterectomy, or those who are menopausal (defined as absence of a menstrual cycle for at least 12 consecutive months). The reason for exemption should be recorded in the medical history.

# 8.5. Pharmacokinetic Testing

## 8.5.1. Seribantumab PK Samples

Blood samples will be collected from all patients to determine the levels of monoclonal antibodies that comprise seribantumab. The serum PK analysis will be performed post-dose on Cycle 1, Week 1, and pre-dose for all subsequent seribantumab infusions until the completion of Cycle 2, as outlined in Table 4. Approximately 5 mL of blood will be collected. The real time of blood collection must be documented in the respective eCRF. A laboratory manual will be provided with instructions for collecting, processing, and shipping the samples.

PK samples should be collected at the following time-points relative to the seribantumab infusion:

**Table 4: Seribantumab PK Collection Timepoints** 

Seribantumab PK Sample	Pre-infusion	Post-infusion
Cycle 1, Week 1		X
Cycle 1, Week 3	X	
Cycle 2, Week 1	X	
Cycle 2, Week 3	X	

#### 8.5.2. Fulvestrant PK samples

To determine the levels of fulvestrant, blood samples will be collected for all patients prior to the seribantumab dose on Cycle 1, Week 1, Cycle 1, Week 3, Cycle 2, Week 1, and Cycle 2, Week 3

Approximately 5 mL of blood will be collected. The real time of blood collection must be documented in the respective eCRF. A laboratory manual will be provided with instructions for collecting, processing, and shipping the samples.

## 8.6. Anti-Seribantumab Immunogenicity

Serum samples will be collected to determine the presence of an immunologic reaction to seribantumab (i.e. human anti-human antibodies; HAHA). A laboratory manual will be provided with instructions for collecting, processing, and shipping these samples.

### 8.7. Biomarker Samples

Biomarker data will be explored from collected tissue and serum samples to assess potential associations with tumor response. To help further understand the biological phenotype of heregulin-positive ER/PR+ and HER2 negative breast cancer, these samples will be used to assess the mRNA and/or protein for clinically relevant biomarkers for breast cancer, including ErbB receptors, cMET, IGF-1R, and FGF receptor tyrosine kinases and their respective ligands (ErbB ligands, HGF, IGFs and FGFs). Efficacy outcomes considered for pre-specified mechanistic biomarker analysis will include OS, PFS, and ORR.

# 8.7.1. Tissue for HRG eligibility assessment

The most recent available tumor tissue available from anytime between diagnosis and signing consent for this trial can be used for HRG testing. If no tissue is available, patients can undergo a fresh tissue biopsy, (either a CNB or FNA) to determine eligibility and are also asked to submit a second pass/ core or second aspirate for research purposes if possible. Directions for processing and shipping the tissue sample for heregulin testing can be found in the laboratory manual.

# 8.7.2. Tumor Biopsy

Prior to receiving the first dose of study drug, all HRG positive patients should provide one fresh tumor biopsy for research purposes. This biopsy will be used to confirm HRG status, and samples will be used to conduct exploratory studies to further characterize and correlate possible biomarkers that may help to predict or evaluate response to seribantumab. Patients who undergo a fresh tumor sample for eligibility testing do not need to provide an additional sample.

## 8.7.3. Serum Samples

Serum samples will be collected at time points described in Section 6.1. Serum will be collected from all patients. The samples will be used to conduct exploratory studies to further characterize and correlate possible biomarkers that may help to predict or evaluate response to seribantumab. In the event that there is remaining sample available after conducting these analyses, it will be stored and used by the Sponsor for future biomarker analysis. At the time of informed consent, patients will be able to refuse storage of these remaining samples. Directions for processing and shipping the samples can be found in the laboratory manual.

# 8.7.4. ESR1 Testing

Plasma samples will be collected at time points described in Section 6.1 from all patients. These samples will be used to test for the ESR1 mutation in order to further characterize and correlate whether these mutations may help to predict or evaluate response to seribantumab. Directions for processing and shipping these samples can be found in the laboratory manual.

#### 8.7.5. Archived Tumor Samples

If available, formalin-fixed paraffin embedded tumor samples (either a tumor block or freshly cut slides) obtained at the time of diagnosis will be collected to compare a patients HRG status with

the screening tissue sample if different, for example, a fresh biopsy of a metastatic lesion. Directions and requirements for processing and shipping the archived tumor samples can be found in the laboratory manual.

# 9. Adverse Event and Hospitalization Reporting

#### 9.1. Definitions

#### 9.1.1. Adverse Events

An adverse event is any untoward medical occurrence in a patient or clinical investigation patient administered a pharmaceutical product and which does not necessarily have to have a causal relationship with this treatment. An adverse event can therefore be any unfavorable and unintended sign, including abnormal laboratory findings, symptoms, or diseases temporally associated with the use of a medicinal product, whether or not considered related to the medicinal product.

#### 9.1.2. Serious Adverse Event

A serious adverse event (SAE) is any untoward medical occurrence that at any dose:

- Results in death
- Is life-threatening (an event in which the patient was at risk of death at the time of the event; it does not refer to an event which hypothetically might have caused death if it were more severe)
- Requires in-patient hospitalization or prolongation of existing hospitalization (Exception: hospitalization for elective treatment of a pre-existing condition that did not worsen during the study is not considered an adverse event. NOTE: Complications that occur during hospitalization are adverse events and if a complication prolongs hospitalization, then the event is serious);
- Results in persistent or significant disability/incapacity
- Is a congenital anomaly or birth defect
- Other important medical events that may not be immediately life-threatening or result in death or hospitalization but may jeopardize the patient or may require intervention to prevent one of the outcomes listed above. Examples of such events are intensive treatment in an emergency room for allergic bronchospasm; blood dyscrasias or convulsions that do not result in hospitalization; or development of drug dependency or drug abuse.

While the term "severe" is often used to describe the intensity (severity) of an event, the event itself may be of relatively minor significance (such as a severe headache). This is not the same as "serious", which is based on a patient/event outcome or action criteria usually associated with events that pose a risk to a patient's life or functioning.

#### 9.1.2.1. Progressive Disease

Because of the natural history of metastatic breast cancer, the vast majority of patients will progress on treatment due to their underlying condition, resulting in hospitalization, appropriate medical care or death. Therefore, progression of underlying malignancy will not be recorded and reported as an adverse event or serious adverse event. In the event that the investigator is unsure

whether or not an AE is a result of the underlying malignancy, the AE should be submitted as a serious adverse event if it meets the appropriate seriousness criteria.

### 9.2. Assessing and Documenting Adverse Events and Hospitalizations

Adverse event assessment will begin in conjunction with informed consent. Investigators should complete all routine and standard of care assessments to evaluate for toxicity and symptoms of drug-induced adverse events. This may include, but is not limited to, verbal reports from the patient and/or caregiver, physical examination and laboratory findings.

For all patients between informed consent and eligibility determination and for heregulin positive patients during their time on study, all adverse events, whether serious or not, will be described in the source documents and the adverse event page of the case report form. All new events, as well as those that worsen in intensity or frequency relative to baseline, which occur after first administration of study drug through the first Overall Survival follow-up visit or phone call, must be reported. However, new adverse events felt by the investigator to be related to study treatment, must be reported any time the investigator becomes aware of such an event, even if this occurrence is after the first Overall Survival follow-up. All adverse events should be followed until resolution, or until the patient discontinues from the overall survival follow-up portion of the study.

Laboratory, vital signs or ECG abnormalities are to be recorded as Adverse Events only if they are medically relevant: symptomatic, requiring corrective treatment, leading to discontinuation and/or fulfilling a seriousness criterion.

Information to be reported in the description of each adverse event includes:

- A medical diagnosis of the event (if a medical diagnosis cannot be determined, a description of each sign or symptom characterizing the event should be recorded)
- The date of onset of the event
- The date of resolution of the event
- A determination of whether the event is serious or not
- A determination of relatedness to the study drug
- Action taken with study drug: none; change in the study drug administration (e.g., temporary interruption in dosing); drug treatment required; non-drug treatment required; diagnostic or concomitant procedure performed; patient discontinued from the study (complete Treatment Termination case report form)
- Outcome: resolved without sequelae; resolved with sequelae; event ongoing; subject died (notify the Sponsor immediately, and complete the Serious Adverse Event page and the Subject Death page)

### 9.2.1. Hospitalizations

Information on patient hospitalizations and/or unscheduled hospital visits should be collected in the eCRF, whether or not associated with an adverse event.

#### 9.3. Reporting Serious Adverse Events

Serious adverse events (SAE) will not be reported for patients who only sign the pre-screening consent form or for heregulin negative patients unless the serious event is directly related to a study procedure (i.e. tumor biopsy). Serious adverse event reporting will begin in conjunction

with the date of signing the main study informed consent. Any SAEs occurring prior to study drug administration that the investigator believes may have been caused by a protocol procedure must be reported immediately to the Sponsor or its designee and recorded on the case report form. Serious adverse event reporting for HRG negative patients is not required unless the event is directly related to a procedure performed for this trial.

All fatal or life-threatening adverse events must be immediately reported to the Sponsor or CRO's medical team by telephone or e-mail. Within 24 hours of the event, the Serious Adverse Event Form must be faxed to the Drug Safety Manager whether full information regarding the event is known or not. Additional follow-up by the investigator will be required if complete information is not known. De-identified source documentation of all examinations, diagnostic procedures, etc. which were completed with respect to the event should be included with the SAE form. Care should be taken to ensure that the patient's identity is protected and the patient's identifiers (as assigned at the time of study enrollment) are properly mentioned on any copy of source document provided to the Sponsor. For laboratory results, include the laboratory normal ranges.

In case of accidental or intentional overdose of study drug (seribantumab or fulvestrant), even if asymptomatic or not fulfilling a seriousness criterion, the overdose is to be reported to the Sponsor or Medical Monitor immediately (within 1 working day) using the AE and SAE forms. Overdose of study drug will be defined as  $\geq$ 3300 mg of seribantumab, or  $\geq$ 133% of planned dose of fulvestrant.

All other serious adverse events must be reported to the Drug Safety Manager within 24 hours by phone, e-mail or fax. Details are outlined in the study procedure manuals. The Serious Adverse Event Form must also be faxed to the Drug Safety Manager within 24 hours of the event whether full information regarding the event is known or not. Additional follow-up by the investigator will be required if complete information is not known.

The Medical Monitor shall be contacted as deemed necessary by the site. Current contact information shall be maintained at the site within the regulatory binder.

All serious adverse events (SAEs) will be evaluated by the Medical Monitor. If meeting the requirements for expedited reporting, the Sponsor will report the adverse event to all regulatory authorities with jurisdiction over ongoing trials with the study drug and to all other investigators involved in clinical trials with the study drug. The investigator is responsible for reporting all SAEs to the appropriate IRB/EC.

# 9.4. Determining the Severity and Relatedness of an Event

### 9.4.1. Grading the Severity of an Adverse Event

Each adverse event will be graded according to the NCI CTCAE V 4.03. For events not listed in the CTCAE, severity will be designated as mild, moderate, severe, or life-threatening, or fatal which correspond to Grades 1, 2, 3, 4, and 5, respectively on the NCI CTCAE, with the following definitions:

- **Mild:** an event not resulting in disability or incapacity and which resolves without intervention:
- **Moderate:** an event not resulting in disability or incapacity but which requires intervention:

- **Severe:** an event resulting in temporary disability or incapacity and which requires intervention:
- **Life-threatening:** an event in which the patient was at risk of death at the time of the event
- Fatal: an event that results in the death of the patient

# 9.4.2. Relatedness to Study Drug

The investigator must attempt to determine if there exists reasonable possibility that an adverse event is related to the use of one or more study drugs, according to the following guidelines:

- Unrelated: This category is applicable to those AEs that are clearly due to extraneous causes (concurrent drugs, environment, etc.) and/or the clinically plausible temporal sequence is inconsistent with the onset of the event and the administration of the study drug and do not meet the criteria for drug relationship listed under UNLIKELY, POSSIBLY, PROBABLY, DEFINITELY RELATED or UNKNOWN.
- Unlikely: The event is clearly due to causes distinct from the use of the study drug, such as a documented pre-existing condition, the effect of a concomitant medication a new condition which, based on the pathophysiology of the condition, and the pharmacology of the study drug, would be unlikely related to the use of the study drug
- **Possible:** The event follows a reasonable temporal sequence from administration of the study drug AND the event follows a known pathological response pattern to the study drug BUT the event could have been produced by an intercurrent medical condition which, based on the pathophysiology of the condition, and the pharmacology of the study drug, would be unlikely related to the use of the study drug or the event could be the effect of a concomitant medication
- **Probable:** The event follows a reasonable temporal sequence from administration of the study drug and the event follows a known response pattern to the study drug AND the event cannot have been reasonably explained by an intercurrent medical condition or the event cannot be the effect of a concomitant medication
- **Definite**: The event follows a reasonable temporal sequence from administration of the study drug, the event follows a known response pattern to the study drug and based on the known pharmacology of the study drug, the event is clearly related to the effect of the study drug
- Unknown: Based on the evidence available, causality cannot be ascribed

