# 1.5.3.1. Previous Safety Experience of Seribantumab in Combination with Endocrine Therapies

Seribantumab has been combined with exemestane in one previous placebo-controlled study, and 56 patients were dosed with the combination. In this study, the most frequently reported adverse events (reported in  $\geq$ 15% of patients) regardless of relationship included (treatment arm % vs. control arm %): diarrhea (50.0% vs 23.7%), nausea (28.6% vs 23.7%), fatigue (25.0% vs 23.7%), arthralgia (21.4% vs 20.3%), cough (16.1% vs 16.9%), and decreased appetite (16.1% vs 10.2%). The most frequently reported adverse events (reported in  $\geq$ 15% of patients) that were assessed by the Investigator to be related to seribantumab include: diarrhea (37.5% vs 11.9%), fatigue (19.6% vs 13.6%), and nausea (16.1% vs 18.6%).

[figure not shown]
Serious adverse events were reported in 7 patients (12.5%) on the seribantumab plus exemestane arm compared to 11 patients (18.6%) on the control arm. The most frequently reported serious event on the seribantumab containing arm was nausea, occurring in 2 patients (3.6%).

Seribantumab has not been combined with fulvestrant in other clinical studies. It is expected that seribantumab will continue to combine well with endocrine agents and with no expected increases in frequencies of severe or serious adverse events. Increased reports of mild to moderate AEs may be observed for diarrhea, nausea, vomiting, and fatigue.

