## 5.2.5. Management of Toxicity Related to Seribantumab

In the event that a patient experiences a toxicity  $\geq$  Grade 3 that is not an IRR and is possibly, probably or definitively related to seribantumab treatment, and not related to fulvestrant, it is at the investigator's discretion to hold dosing or discontinue treatment with seribantumab. Prior to holding the dose or discontinuing treatment, the investigator must notify the sponsor and Medical Monitor.

In the event that seribantumab treatment has been held for 28 consecutive days, the patient should be discontinued. No dose reductions for seribantumab are permitted.

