#### 5.6.2 Adverse Events

Adverse events will be coded using the latest MedDRA dictionary at the time of coding. NCI CTCAE v4.0 will be used to grade severity. Frequencies and percentages will be reported by System Organ Class (SOC) and preferred term (PT). Patients with multiple events for a category will be counted once in the highest CTCAE classification. Summary tables will include treatment-emergent AEs, unless specified otherwise. Treatment-emergent adverse events (TEAEs) will be defined as patients based on the event onset date relative to first dose of study drug in the study. Missing onset date for an event will be considered as TEAE. Adverse events with a starting date 30 or more days after the last dose date are not considered TEAEs. Relatedness will be considered: Possibly, Probably, or Definitely related per case report form classification. If relatedness is missing the adverse event will be considered TEAE. The order of reporting the events in summary tables will be according to the following where applicable:

- SOC will be alphabetically reported
- Descending order of frequencies according to the number of patients in the seribantumab treatment group experiencing an adverse event
- PT will be alphabetically reported

The following tables will be reported:

- TEAE
  - Any TEAE by SOC
  - Any TEAE by SOC and PT\*
  - Any TEAE by PT
  - Any TEAE by PT by NCI CTCAE Grade
  - Any TEAE by PT by cycle

- Any TEAE by PT by NCI CTCAE Grade by cycle
- Related TEAE
  - Any TEAE by SOC and PT\*
  - Any TEAE by PT
  - Any TEAE by PT by NCI CTCAE Grade
- TEAE NCI CTCAE Grade 3 or higher
  - Any TEAE by SOC and PT
  - Any TEAE by PT
- Related TEAE NCI CTCAE Grade 3 or higher
  - Any TEAE by SOC and PT
  - Any TEAE by PT
- SAE TEAEs only
  - Any SAE by SOC and PT\*
  - Any SAE by PT
- TEAE Various
  - Any TEAE Resulting in Dose Reduction
  - Any TEAE Resulting in Treatment Discontinuation
  - Any TEAE Resulting in Death

In the AE preferred term summary tables, a patient having multiple events within a System Organ Class is counted only once for that SOC. Similarly, a patient having multiple events under a preferred term is counted only once for that PT. Listings will be provided for all adverse event data.

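### Protocol 9.4.2 asks for a reasonable possibility of causality, but all three related categories require an already known response pattern, so a new type of event can fit only Unknown

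*Protocol*

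**What the plan says.** Protocol 9.4.2 tells the investigator to "determine if there exists reasonable possibility that an adverse event is related to the use of one or more study drugs" and offers six categories as guidelines for doing so:

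- *Possible*: reasonable timing "AND the event follows a known pathological response pattern to the study drug BUT the event could have been produced by an intercurrent medical condition" or could be the effect of another medication.
- *Probable*: reasonable timing, and "the event follows a known response pattern to the study drug AND the event cannot have been reasonably explained" by another condition or medication.
- *Definite*: reasonable timing, and "the event follows a known response pattern to the study drug and based on the known pharmacology of the study drug" a clear drug effect.
- *Unlikely*: a clear cause other than the drug.
- *Unrelated*: a clear extraneous cause and/or timing that does not fit, with none of the other five categories met.
- *Unknown*: the evidence does not allow an attribution.

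Relatedness is then used in four places:

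- Protocol 5.2.5, on toxicity of Grade 3 or higher other than infusion reactions, covers events "possibly, probably or definitively related to seribantumab treatment, and not related to fulvestrant".
- Protocol 9.2 says of the period after the first survival contact that "new adverse events felt by the investigator to be related to study treatment, must be reported any time" the investigator learns of them.
- Protocol 10.5.4 plans tables of TEAEs related to seribantumab or fulvestrant, without saying which categories count.
- SAP 5.6.2 states: "Relatedness will be considered: Possibly, Probably, or Definitely related per case report form classification".

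On prior experience, Protocol 1.5.3.1 says: "Seribantumab has not been combined with fulvestrant in other clinical studies". Protocol 2.2 makes describing the safety of the combination a secondary objective.

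**The concern.** The instruction and the definitions under it set different tests. The instruction needs only a reasonable possibility. The three categories that express a drug relation also need the event to match something already known about the drug. The two categories that deny a relation need a clear other cause, or for *Unrelated* timing that does not fit. Between them lies an event of a new type, with plausible timing and no clear other cause.

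A first study of a combination has a particular interest in that kind of event. If its only available label is one that the related-event summaries do not count, those summaries are weakest where prior knowledge is thinnest. Sites may also differ: one follows the instruction and codes the event *Possible*, another follows the definitions and codes it *Unknown*.

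**Working it through.** The plan gives no figure on this point and no arithmetic applies. The check tests each definition against three types of event, then sees where the result is used.

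**Step 1. What the pattern must be known for.** The condition refers to the study drug, and Protocol 9.3 uses that term for seribantumab or fulvestrant. The question is therefore whether the event type is known for either drug, not whether it is known for the pair.

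**Step 2. Three test events, all with plausible timing.**

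- A: a type not known for either drug, no other cause in view.
- B: a type not known for either drug, another cause possible but not clear.
- C: a type known for one of the drugs, but more severe or more frequent than expected, no other cause in view.

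| Category | A | B | C |
|---|---|---|---|
| *Possible* | Fails: no known pattern | Fails: no known pattern | Not the best fit: no alternative cause |
| *Probable* | Fails: no known pattern | Fails: no known pattern, and another cause is possible | Fits |
| *Definite* | Fails: no known pattern | Fails: no known pattern | Depends on the pharmacology |
| *Unlikely* | Fails: no clear other cause | Fails: other cause not clear | Fails |
| *Unrelated* | Fails: timing fits, no clear other cause | Fails: timing fits, other cause not clear | Fails |
| *Unknown* | Fits | Fits | Not needed |

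For A and B, 3 of 3 related categories and 2 of 2 non-related categories are closed, leaving 1 of 6. In each related category the pattern condition is joined by a conjunction to the timing condition, so it is mandatory and not one factor among several. C shows the limit of the problem: an event that is unexpected only in degree still qualifies.

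**Step 3. Where *Unknown* goes.**

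- Protocol 5.2.5 names three related categories; *Unknown* is not one of them.
- SAP 5.6.2 names the same three. It has a rule for missing relatedness but none for *Unknown*.
- Protocol 10.5.4 does not define related. If the same three categories are used, A and B are left out of the related tables.
- Protocol 9.2 rests on what the investigator feels and does not cite the 9.4.2 categories. The outcome therefore depends on whether a site carries the definitions over.

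The supplied SAP identifies itself with a different protocol number and describes a phase 3 trial with exemestane or fulvestrant. It is supporting evidence only; the gap itself follows from Protocol 9.4.2 alone.

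**The case against.** The strongest reply is that the definitions are offered as guidelines under a reasonable-possibility instruction, so an investigator may use judgement and code a new event as *Possible*. That is true, and it means the problem holds for the definitions as written and not for every site's practice. It does not remove the inconsistency, because a site that follows the definitions reaches a different answer from one that follows the instruction.

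The second reply is that little depends on the label, and much of this stands. Protocol 9.2 collects adverse events regardless of causality through the first survival contact. Protocol 9.3 requires on-study SAE reports without a relatedness filter, and the Medical Monitor evaluates all SAEs. Protocol 10.5.4 tabulates all TEAEs and lists every event. Under Protocol 10.6 an unblinded DMC monitors safety, and a comparison of all events between arms does not need investigator causality. Protocol 5.2.5 gives the investigator discretion, and Protocol 4.4 lists an adverse event or an investigator decision as a reason for withdrawal without any relatedness condition.

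A reader might therefore infer more than the documents support:

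- *New signals would be screened out, or expedited reporting would be blocked.* Given the routes above, they would not be. Protocol 9.3 does not tie the expedited assessment to the investigator's category.
- *An event can no longer be both related and unexpected.* Event C shows that it can.
- *Any interaction toxicity must lack a known pattern.* An interaction that amplifies a known effect of either drug meets the condition. Protocol 5.2.5.1 already lists expected effects of the combination, and Protocol 1.5.3 reports 700 patients exposed to seribantumab.

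**Conclusion.** The point holds as an inconsistency inside Protocol 9.4.2 with a limited effect. For an event of a type not known for either drug, with plausible timing and no clear other cause, the written definitions leave *Unknown* as the only category. The consequence is possible omission from the related-TEAE tables and uneven handling under the relatedness wording of Protocol 5.2.5 and 9.2. It is not loss of the events.

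The conclusion rests on two assumptions: that sites apply the definitions as written, and that Protocol 10.5.4 will count the same three categories as 5.2.5 and SAP 5.6.2. The documents give no basis for estimating how many events would be affected. Because the combination is new and its safety profile is a stated objective, the wording should be corrected.

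**What to change.** In Protocol 9.4.2, stop requiring a known response pattern for *Possible* and *Probable*, so that the categories carry out the section's own instruction:

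- *Possible*: reasonable timing and a reasonable possibility of a causal role, whether or not the event type is already described for the drug, and even if another cause could also explain it.
- *Probable*: reasonable timing, and no other cause that reasonably explains the event.
- *Definite*: keep known pattern and pharmacology as required conditions. For the other two they become supporting evidence.

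With this wording event A falls under *Probable*. Event B falls under *Possible* when the investigator sees a reasonable possibility. The threshold for *Possible* should stay at reasonable possibility. The weaker test that a causal role cannot be excluded would go below the protocol's own standard and could bring in many background events of the disease.

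Align the eCRF completion guide, and state in Protocol 10.5.4 and the SAP which categories count as related. The relatedness wording in Protocol 5.2.5 and 9.2 should be read against the revised categories; no change to the management of toxicity is proposed here.

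The cost is an edit to the protocol and guide, with somewhat more events classed as related. Because sites are blinded, that increase would be expected in both arms.
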